6.2 Adverse Events (AEs), Serious Adverse Events (SAEs), and Other Reportable Safety Events

The definitions of an AE or SAE, as well as the method of recording, evaluating, and assessing causality of AE and SAE and the procedures for completing and transmitting AE, SAE, and other reportable safety event reports can be found in Appendix 5.

Adverse events, SAEs, and other reportable safety events will be reported by the participant (or, when appropriate, by a caregiver, surrogate, or the participant's legally authorized representative).

The investigator and any designees are responsible for detecting, documenting, and reporting events that meet the definition of an AE or SAE as well as other reportable safety events. Investigators remain responsible for following up AEs, SAEs, and other reportable safety events for outcome.

The investigator, who is a qualified physician, will assess events that meet the definition of an AE or SAE as well as other reportable safety events with respect to seriousness, intensity/toxicity and causality.

Olaparib

Any toxicity observed during the course of the study could be managed by interruption of the dose of study treatment or dose reductions. Repeat dose interruptions are allowed as required, for a maximum of 4 weeks on each occasion. If the interruption is any longer, the study team must be informed. Study treatment can be dose reduced to 250 mg twice daily as a first step and to 200 mg twice daily as a second step. If the reduced dose of 200 mg twice daily is not tolerable, no further dose reduction is allowed and study treatment should be discontinued.

Once dose is reduced, escalation is not permitted (except following concomitant treatment with CYP3A4 inhibitors – see Section 6.5

6.2.1 Time Period and Frequency for Collecting AE, SAE, and Other Reportable Safety Event Information

All AEs, SAEs, and other reportable safety events that occur after the consent form is signed but before intervention allocation/randomization must be reported by the investigator if the participant is receiving placebo run-in or other run-in treatment, if the event cause the participant to be excluded from the study, or is the result of a protocol-specified intervention, including but not limited to washout or discontinuation of usual therapy, diet, or a procedure.

- All AEs from the time of intervention allocation/randomization through 30 days following cessation of study intervention must be reported by the investigator.
- All AEs meeting serious criteria, from the time of intervention allocation/randomization through 90 days following cessation of study intervention or 30 days following cessation of study intervention if the participant initiates new anticancer therapy, whichever is earlier, must be reported by the investigator.
- All pregnancies and exposure during breastfeeding, from the time of intervention allocation/randomization through 120 days following cessation of study intervention, or 30 days following cessation of study intervention if the participant initiates new anticancer therapy must be reported by the investigator.
- Additionally, any SAE brought to the attention of an investigator at any time outside of the time period specified above must be reported immediately to Merck if the event is considered drug-related.

Investigators are not obligated to actively seek AEs or SAEs or other reportable safety events in former study participants. However, if the investigator learns of any SAE, including a death, at any time after a participant has been discharged from the study, and he/she considers the event to be reasonably related to the study intervention or study participation, the investigator must promptly notify Merck.

All initial and follow-up AEs, SAEs, and other reportable safety events will be recorded and reported to Merck within the time frames as indicated in Table 11.

Table 11 Reporting Time Periods and Time Frames for Adverse Events and Other Reportable Safety Events

Type of Event	Reporting Time Period: Consent to Randomization/Allocation	Reporting Time Period: Randomization/Allocation through Protocol-specified Follow-up Period	Reporting Time Period: After the Protocol-specified Follow-up Period	Time Frame to Report Event and Follow-up Information to Merck:
Serious Adverse Event (SAE) including Cancer and Overdose	Report if: - due to protocol-specified intervention - causes exclusion - participant is receiving placebo run-in or other run-in treatment	Report all	Report if: - drug/vaccine related. (Follow ongoing to outcome)	Within 2 business days but no longer than 3 calendar days of learning of event
Pregnancy/Lactation Exposure	Report if: - due to intervention - causes exclusion	Report all	Previously reported – Follow to completion/termination; report outcome	Within 2 business days but no longer than 3 calendar days of learning of event
Event of Clinical Interest (require regulatory reporting)	Report if: - due to intervention - causes exclusion	Report - potential drug-induced liver injury (DILI) - require regulatory reporting	Not required	Within 2 business days but no longer than 3 calendar days of learning of event

6.2.1.1 Management of hematological toxicity

Management of anemia

Table 12 Management of anemia

Hemoglobin	Action to be taken
Hb < 10 but \geq 8 g/dl (CTCAE Grade 2)	
First occurrence: Give appropriate supportive treatment and investigate causality. Investigator judgement to continue olaparib with supportive treatment (eg transfusion) or interrupt dose for a maximum of 4 weeks. Study treatment can be restarted if Hb has recovered to > 9 g/dl.
 
Subsequent occurrences: If Hb < 10 but \geq 9 g/dl investigator judgement to continue olaparib with supportive treatment (eg transfusion) or dose interrupt (for max of 4 weeks) and upon recovery dose reduction may be considered (to 250 mg twice daily as a first step and to 200 mg twice daily as a second step). If Hb < 9 but \geq 8 g/dl, dose interrupt (for max of 4 weeks) until Hb \geq 9 g/dl and upon recovery dose reduction may be considered (to 250 mg twice daily as a first step and to 200 mg twice daily as a second step).

Hb < 8 g/dl (CTCAE Grade 3)	
Give appropriate supportive treatment (e.g. transfusion) and investigate causality. Interrupt olaparib for a maximum of 4 weeks until improved to Hb \geq 9 g/dl. Upon recovery dose reduce to 250 mg twice daily as a first step and to 200 mg twice daily as a second step in the case of repeat Hb decrease.

Common treatable causes of anemia (e.g., iron, vitamin B12 or folate deficiencies and hypothyroidism) should be investigated and appropriately managed. In some cases, management of anemia may require blood transfusions. For cases where patients develop prolonged hematological toxicity (\geq 2 week interruption/delay in study treatment due to CTC grade 3 or worse anemia and/or development of blood transfusion dependence), refer to guidance later in this section for the management of this.

Management of neutropenia, leukopenia and thrombocytopenia

Table 13 Management of neutropenia, leukopenia and thrombocytopenia

Toxicity	Study treatment dose adjustment
CTCAE Grade 1-2	Investigator judgement to continue treatment or if dose interruption, this should be for a maximum of 4 weeks; appropriate supportive treatment and causality investigation
CTCAE Grade 3-4	Dose interruption until recovered to CTCAE gr 1 or better for a maximum of 4 weeks. If repeat CTCAE grade 3-4 occurrence, dose reduce olaparib to 250 mg twice daily as a first step and 200 mg twice daily as a second step

Adverse event of neutropenia and leukopenia should be managed as deemed appropriate by the investigator with close follow up and interruption of study drug if CTC grade 3 or worse neutropenia occurs.

Primary prophylaxis with Granulocyte colony-stimulating factor (G-CSF) is not recommended, however, if a patient develops febrile neutropenia, study treatment should be stopped and appropriate management including G-CSF should be given according to local hospital guidelines. Please note that G-CSF should not be used within at least 24 h (7 days for pegylated G-CSF) of the last dose of study treatment unless absolutely necessary.

Platelet transfusions, if indicated, should be done according to local hospital guidelines.

For cases where patients develop prolonged hematological toxicity (≥ 2 week interruption/delay in study treatment due to CTC grade 3 or worse), refer to guidance later in this section for the management of this.

Management of prolonged hematological toxicities while on study treatment

If a patient develops prolonged hematological toxicity such as:

- ≥ 2 week interruption/delay in study treatment due to CTC grade 3 or worse anaemia and/or development of blood transfusion dependence
- ≥ 2 week interruption/delay in study treatment due to CTC grade 3 or worse neutropenia (ANC $< 1 \times 10^9/L$)
- ≥ 2 week interruption/delay in study treatment due to CTC grade 3 or worse thrombocytopenia and/or development of platelet transfusion dependence (Platelets $< 50 \times 10^9/L$)

Check weekly differential blood counts including reticulocytes and peripheral blood smear. If any blood parameters remain clinically abnormal after 4 weeks of dose interruption, the patient should be referred to hematologist for further investigations. Bone marrow analysis and/or blood cytogenetic analysis should be considered at this stage according to standard hematological practice. Study treatment should be discontinued if blood counts do not recover to CTC gr 1 or better within 4 weeks of dose interruption.

Development of a confirmed myelodysplastic syndrome or other clonal blood disorder should be reported as an SAE and full reports must be provided by the investigator to AstraZeneca Patient Safety. Olaparib treatment should be discontinued if patient's diagnosis of MDS and/or AML is confirmed.

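### After an interruption of 2 weeks or more for grade 3 anemia, Table 12 and the prolonged-toxicity text set different hemoglobin levels for recovery, and at 4 weeks with Hb 9 to below 10 g/dl they give opposite instructions

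*Combined protocol and SAP*

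**What the plan says.** Section 6.2.1.1 deals with anemia in two places.

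Table 12 grades and manages anemia by hemoglobin. One row is labeled "Hb < 10 but \geq 8 g/dl (CTCAE Grade 2"), the next "Hb < 8 g/dl (CTCAE Grade 3"). For the grade 3 row the instruction is "Interrupt olaparib for a maximum of 4 weeks until improved to Hb" of at least 9 g/dl, followed by "Upon recovery dose reduce to 250 mg twice daily as a first step and to 200 mg twice daily as a second step" if the hemoglobin falls again. The text below the table covers cases where grade 3 or worse anemia delays treatment by 2 weeks or more, or where transfusion dependence develops. For these it tells sites to "refer to guidance later in this section for the management of this".

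That later guidance is the paragraph on prolonged hematological toxicities. Its anemia trigger is an interruption of at least 2 weeks, worded as a "week interruption/delay in study treatment due to CTC grade 3 or worse anaemia and/or development of blood transfusion dependence". It asks for weekly counts, for referral to a hematologist if values are still abnormal after 4 weeks, and then states: "Study treatment should be discontinued if blood counts do not recover to CTC gr 1 or better within 4 weeks of dose interruption".

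Table 13, for neutropenia, leukopenia and thrombocytopenia, uses recovery to grade 1 or better within 4 weeks, the same criterion as the prolonged-toxicity paragraph. Only the anemia table uses a different level.

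**The concern.** Both texts cover the same event (an interruption for grade 3 anemia), share a 4-week limit and turn on recovery. They define recovery differently: Table 12 by an absolute hemoglobin of 9 g/dl, the prolonged-toxicity paragraph by grade. By Table 12's own labels, 9 g/dl is still grade 2. A patient can therefore have recovered under one text and not under the other.

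Sections 2.0 and 4.2.2 single out persistent grade 3 or higher anemia for extra attention because of myelodysplastic syndromes reported with olaparib, so this is a safety rule that sites need to apply in the same way. Section 2.1 describes the trial as multi-center. The same hemoglobin value could be handled as a dose reduction at one site and as a discontinuation at another. That would carry into the safety summaries planned in section 7.2: adverse events leading to interruption, modification or discontinuation, dose reductions, and relative dose intensity.

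**Working it through.** No figure in the statistical plan bears on this, so the check sets the two rules side by side.

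Inputs, all from section 6.2.1.1:
- Grade 2 anemia is Hb 8 to below 10 g/dl (Table 12). Grade 1 or better is therefore Hb of at least 10 g/dl.
- Grade 3 is Hb below 8 g/dl (Table 12).
- Table 12 allows restart at a reduced dose once Hb is at least 9 g/dl, within at most 4 weeks.
- The prolonged-toxicity text is triggered by an interruption of at least 2 weeks for grade 3 or worse anemia, and/or transfusion dependence.
- Once triggered, it requires grade 1 or better within 4 weeks, otherwise discontinuation.

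The two recovery levels are 9 and 10 g/dl, so the disputed band is 10 − 9 = 1 g/dl wide, from 9.0 to just under 10. For a patient interrupted because Hb fell below 8, without transfusion dependence:

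| Weeks interrupted | Hb now (g/dl) | Table 12 | Prolonged-toxicity text | Result |
|---|---|---|---|---|
| Under 2 | 9 or more | Resume, reduced dose | Not triggered | No conflict |
| 2 to below 4 | Below 9 | Stay interrupted | Grade 1 still awaited | No conflict |
| 2 to below 4 | 9 to below 10 | Resume, reduced dose | Grade 1 still required by week 4 | Unclear |
| 2 to below 4 | 10 or more | Resume, reduced dose | Grade 1 reached | Agree |
| 4 | Below 9 | Restart level not met, maximum interruption reached | Discontinue | Neither allows restart |
| 4 | 9 to below 10 | Resume, reduced dose | Discontinue | Directly opposite |
| 4 | 10 or more | Resume, reduced dose | Grade 1 reached | Agree |

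The unclear row arises because the 4-week test is counted from the dose interruption. Take a patient at Hb 9.5 in week 3. Table 12 lets her restart, which ends the interruption. The prolonged-toxicity text does not say whether she must then stop if she is still at 9.5 in week 4, or whether the test lapsed when she restarted.

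**The case against.** The strongest reply is that the section is tiered. Table 12 is the general rule, and the sentence below it sends prolonged cases to the later text, so that text alone governs once 2 weeks have passed. The reading is reasonable, and a careful site might adopt it. It is implied, though, not stated. The cross-reference does not say that the restart level of 9 g/dl lapses at 2 weeks, and Table 12 itself runs that level out to 4 weeks, across the whole period the later text covers. Nor does the grade 3 row leave the matter to investigator judgment, as the grade 2 row does in part.

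The objections on scope do stand. A reader might infer that every grade 3 anemia episode, or every interruption of 2 to 4 weeks that recovers to 9.0–9.9 g/dl, meets opposite instructions. The documents do not support that. Episodes recovering in under 2 weeks without transfusion dependence fall under Table 12 alone, and before week 4 the later text does not yet order discontinuation.

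A reader might also take the entry limit in Table 1 of section 5.1.1 (Hb at least 9.0 g/dl) as a further contradiction. It is not: an entry limit and a stopping rule after prolonged grade 3 toxicity serve different purposes and may differ. The entry limit is only context, in that a patient enrolled at 9.0–9.9 could return to her own baseline and still fall short of grade 1.

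**Conclusion.** The inconsistency is real and narrow. It requires grade 3 anemia, an interruption of at least 2 weeks (or transfusion dependence), and Hb of 9 to below 10 g/dl. At the 4-week limit the two texts are directly opposed. In weeks 2 to below 4 the later text leaves open what happens to a patient already restarted. The number of the 48 patients who would fall in this group cannot be derived from the documents.

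The consequences are for patient safety and for the descriptive summaries of discontinuation, dose modification and relative dose intensity in section 7.2. It would be tempting to say that these summaries are the secondary tolerability endpoint. Section 3.2 names that endpoint only as toxicities associated with the regimen, and section 7.2 attaches no test or threshold to the summaries. Nothing in the documents shows an effect on the primary rule of 10 or more responses in 48 patients.

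The conclusion rests on two readings: that the grades in the prolonged-toxicity text follow the bands printed in Table 12, and that study treatment there means olaparib. The second fits section 6.2, where the term appears under the olaparib label with the 250 mg and 200 mg steps. This review takes no position on which recovery level is right.

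**What to change.** Reconcile Table 12 with the prolonged-toxicity paragraph in section 6.2.1.1. There are two ways to do this:
- use a single recovery criterion for anemia in both places; or
- keep both criteria and state which text governs once the 2-week trigger (or transfusion dependence) is met, and whether the 4-week grade 1 test still applies to a patient who has already restarted.

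When doing so, check the result against the hemoglobin entry limit in Table 1, so that the handling of patients who enroll at 9.0–9.9 g/dl is intended. The criterion itself is for the sponsor to choose. The cost is protocol wording only; sample size, endpoints and analyses do not change.

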6.2.1.2 Management of non-hematological toxicity

Repeat dose interruptions are allowed as required, for a maximum of 4 weeks on each occasion. If the interruption is any longer than this the study monitor must be informed. Where toxicity reoccurs following re-challenge with study treatment, and where further dose interruptions are considered inadequate for management of toxicity, then the patient should be considered for dose reduction or must permanently discontinue study treatment.

Study treatment can be dose reduced to 250 mg twice daily as a first step and to 200 mg twice daily as a second step. Treatment must be interrupted if any NCI-CTCAE grade 3 or 4 adverse event occurs which the investigator considers to be related to administration of study treatment.

Management of new or worsening pulmonary symptom

If new or worsening pulmonary symptoms (e.g., dyspnea) or radiological abnormalities occur in the absence of a clear diagnosis, an interruption in study treatment dosing is recommended and further diagnostic workup (including a high resolution CT scan) should be performed to exclude pneumonitis.

Following investigation, if no evidence of abnormality is observed on CT imaging and symptoms resolve, then study treatment can be restarted, if deemed appropriate by the investigator. If significant pulmonary abnormalities are identified, these need to be discussed with the Study Physician.

Management of nausea and vomiting

Events of nausea and vomiting are known to be associated with olaparib treatment. These events are generally mild to moderate (CTCAE grade 1 or 2) severity, intermittent and manageable on continued treatment. The first onset generally occurs in the first month of treatment for nausea and within the first 6 months of treatment for vomiting. For nausea, the incidence generally plateaus at around 9 months, and for vomiting at around 6 to 7 months.

No routine prophylactic anti-emetic treatment is required at the start of study treatment; however, patients should receive appropriate anti-emetic treatment at the first onset of nausea or vomiting and as required thereafter, in accordance with local treatment practice guidelines. Alternatively, olaparib tablets can be taken with a light meal/snack (i.e. 2 pieces of toast or a couple of biscuits).

As per international guidance on anti-emetic use in cancer patients (ESMO, NCCN), generally a single agent antiemetic should be considered e.g., dopamine receptor antagonist, antihistamines or dexamethasone.

Interruptions for intercurrent non-toxicity related events

Study treatment dose interruption for conditions other than toxicity resolution should be kept as short as possible. If a patient cannot restart study treatment within 4 weeks for resolution of intercurrent conditions not related to disease progression or toxicity, the case should be discussed with AZ study physician.

All dose reductions and interruptions (including any missed doses), and the reasons for the reductions/interruptions are to be recorded in the eCRF.

Study treatment should be stopped at least 3 days prior to planned surgery. After surgery study treatment can be restarted when the wound has healed. No stoppage of study treatment is required for any needle biopsy procedure.

Study treatment should be discontinued for a minimum of 3 days before a patient undergoes radiation treatment. Study treatment should be restarted within 4 weeks as long as any bone marrow toxicity has recovered.

Because the AEs related to olaparib may include asthenia, fatigue and dizziness, patients should be advised to use caution while driving or using machinery if these symptoms occur.

Table 14 Dose reductions for study treatment

Initial Dose	Following re-challenge post interruption: Dose reduction 1	Dose reduction 2
300 mg twice daily	250 mg twice daily	200 mg twice daily

6.2.1.3 Renal impairment

If subsequent to study entry and while still on study therapy, a patient's estimated CrCl falls below the threshold for study inclusion (≥ 51 ml/min), retesting should be performed promptly.

A dose reduction is recommended for patients who develop moderate renal impairment (calculated creatinine clearance by Cockcroft-Gault equation or based on a 24-hour urine test of between 31 and 50 ml/min) for any reason during the course of the study: the dose of olaparib should be reduced to 200 mg twice daily.

Because the CrCl determination is only an estimate of renal function, in instances where the CrCl falls to between 31 and 50 mL/min, the investigator should use his or her discretion in determining whether a dose change or discontinuation of therapy is warranted.

Olaparib has not been studied in patients with severe renal impairment (creatinine clearance ≤ 30 ml/min) or end-stage renal disease; if patients develop severe impairment or end stage disease is it recommended that olaparib be discontinued.

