Additionally, pharmacology data clearly show target saturation at 200 mg Q3W. First, PK data in KN001 evaluating target-mediated drug disposition (TMDD) conclusively demonstrated saturation of PD-1 in systemic circulation at doses much lower than 200 mg Q3W. Second, a PBPK analysis was conducted to predict tumor PD-1 saturation over a wide range of tumor penetration and PD-1 expression. This evaluation concluded that pembrolizumab at 200 mg Q3W achieves full PD-1 saturation in both blood and tumor.

Finally, population PK analysis of pembrolizumab, which characterized the influence of body weight and other participant covariates on exposure, has shown that the fixed-dosing provides similar control of PK variability as weight based dosing, with considerable overlap in the distribution of exposures from the 200 mg Q3W fixed dose and 2 mg/kg Q3W dose. Supported by these PK characteristics, and given that fixed-dose has advantages of reduced dosing complexity and reduced potential of dosing errors, the 200 mg Q3W fixed-dose was selected for evaluation across all pembrolizumab protocols.

The FDA approved dose for treatment of BRCA positive ovarian and breast cancers [Pujade-Lauraine et al., 2017; Ledermann et al., 2012] of olaparib 300mg orally (PO) twice daily (BID) will be utilized.

The dose of olaparib used in this study is 300 mg twice daily which is the currently approved dose.

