5.0 METHODOLOGY

5.1 Study Population

Diagnosis/Condition for Entry into the Trial

Patients with metastatic or recurrent histologically confirmed cervical carcinoma who have progressed on or after first line standard of care treatment.

Prospective approval of protocol deviations to recruitment and enrollment criteria, also known as protocol waivers or exemptions, is not permitted.

Each patient should meet all of the inclusion criteria and none of the exclusion criteria for this study in order to be assigned to the study intervention. Under no circumstances, can there be exceptions to this rule. Patients who do not meet the entry requirements are screen failures.

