5.1.1 Participant Inclusion Criteria

Participants are eligible to be included in the study only if all of the following criteria apply:

1. Female participants who are at least 18 years of age on the day of signing informed consent with histologically confirmed diagnosis of cervical carcinoma will be enrolled in this study.
2. Cervical cancer is a disease of the female genital tract. No male patients will be enrolled.
3. A female participant is eligible to participate if she is not pregnant (see Appendix 3), not breastfeeding, and at least one of the following conditions applies:
 - a. Not a woman of childbearing potential (WOCBP) as defined in Appendix 3
OR
 - b. A WOCBP who agrees to follow the contraceptive guidance in Appendix 3 during the treatment period and for at least 120 days after the last dose of study treatment.
4. Participant must have recurrent cervical cancer and have a low potential for cure with radiation therapy or surgery alone and:
 - a. May have received up to 2 prior chemotherapy regimens. Platinum sensitizing agents for radiation therapy are considered a chemotherapy regimen.
5. The participant (or legally acceptable representative if applicable) provides written informed consent for the trial, which includes compliance with the requirements and restrictions listed in the informed consent form (ICF) and this protocol.
6. Have measurable disease based on RECIST 1.1. Lesions situated in a previously irradiated area are considered measurable if progression has been demonstrated in such lesions.
7. Have provided archival tumor tissue sample or newly obtained core or excisional biopsy of a tumor lesion not previously irradiated. Formalin-fixed, paraffin embedded (FFPE) tissue blocks are preferred to slides. Newly obtained biopsies are preferred to archived tissue.

8. Have an Eastern Cooperative Oncology Group (ECOG) performance status of 0 to 1. Evaluation of ECOG is to be performed prior to the first dose of treatment.
9. Patient's life expectancy ≥ 16 weeks.
10. Have adequate organ function as defined in the following table (Table 1). Specimens must be collected within 10 days prior to the start of study treatment. Before patients can be enrolled, they must have normal laboratory values as outlined in Table 1. Labs must also fall within normal limits prior to infusion.

Table 1 Adequate Organ Function Laboratory Values

System	Laboratory Value
Hematological	
Absolute neutrophil count (ANC)	$\geq 1500/\mu\text{L}$

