Platelets	$\geq 100\,000/\mu\text{L}$
Hemoglobin	$\geq 9.0\text{ g/dL}$ or $\geq 5.6\text{ mmol/L}^{\text{a}}$
Renal	
Creatinine OR Measured or calculated ^b creatinine clearance (GFR can also be used in place of creatinine or CrCl)	$\leq 1.5 \times \text{ULN}$ OR $\geq 30\text{ mL/min}$ for participant with creatinine levels $>1.5 \times$ institutional ULN
Hepatic	
Total bilirubin	$\leq 1.5 \times \text{ULN}$ OR direct bilirubin $\leq \text{ULN}$ for participants with total bilirubin levels $>1.5 \times \text{ULN}$
AST (SGOT) and ALT (SGPT)	$\leq 2.5 \times \text{ULN}$ ($\leq 5 \times \text{ULN}$ for participants with liver metastases)
Coagulation	
International normalized ratio (INR) OR prothrombin time (PT) Activated partial thromboplastin time (aPTT)	$\leq 1.5 \times \text{ULN}$ unless participant is receiving anticoagulant therapy as long as PT or aPTT is within therapeutic range of intended use of anticoagulants
ALT (SGPT)=alanine aminotransferase (serum glutamic pyruvic transaminase); AST (SGOT)=aspartate aminotransferase (serum glutamic oxaloacetic transaminase); GFR=glomerular filtration rate; ULN=upper limit of normal.	
^a Criteria must be met without erythropoietin dependency and without packed red blood cell (pRBC) transfusion within last 2 weeks.	
^b Creatinine clearance (CrCl) should be calculated per institutional standard.	
Note: This table includes eligibility-defining laboratory value requirements for treatment; laboratory value requirements should be adapted according to local regulations and guidelines for the administration of specific chemotherapies.	

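### Section 6.2.1.3 cites a CrCl entry threshold of 51 mL/min that no eligibility criterion contains, so a patient entering at 31–50 mL/min has no olaparib dose rule

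*Combined protocol and SAP*

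**What the plan says.** **Entry.** Inclusion criterion 10 (Section 5.1.1) applies Table 1: "Before patients can be enrolled, they must have normal laboratory values as outlined in Table 1". Its renal row can be met in two ways. One is creatinine ≤1.5 × ULN, with no CrCl needed. The other, for creatinine above that limit, is CrCl ≥30 mL/min; GFR may stand in for either measure. Footnote b adds "Creatinine clearance (CrCl) should be calculated per institutional standard". Section 5.1 says of the eligibility rules: "Under no circumstances, can there be exceptions to this rule". None of the exclusion criteria in Section 5.1.2 sets a renal limit.

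**On study.** Section 6.2.1.3 covers the case where a patient's "CrCl falls below the threshold for study inclusion (≥ 51 ml/min), retesting should be performed promptly". It recommends olaparib 200 mg twice daily for moderate impairment (CrCl 31–50 by Cockcroft-Gault or 24-hour urine) arising during the study, then leaves any change to the investigator's discretion. It notes that olaparib is unstudied at CrCl ≤30 and recommends stopping it there. Table 3b (Section 5.2.2) gives the same reduction, again for impairment that arises on treatment.

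**Starting dose.** Table 2 (Section 5.2) lists olaparib 300 mg twice daily without renal adjustment, and Section 4.2.2 says "The dose of olaparib used in this study is 300 mg twice daily which is the currently approved dose". The one planned departure is the six-patient safety rule in Sections 2.0 and 4.2.2, which can move later patients to 300 mg once daily.

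**The concern.** The renal section assumes an entry floor that the entry criteria do not impose. If every patient entered at CrCl 51 or above, a dose rule limited to later impairment would be complete, because nobody could start in the 31–50 band. Under Table 1 as written, some can, and the rule misses them.

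What is at stake is starting-dose safety. A patient at CrCl 40 on day 1 starts at 300 mg twice daily, while one who drops to 40 later is recommended 200 mg twice daily. The retest trigger also fails for anyone who entered below 51, since she cannot fall below a level she never reached. Entry and dosing may use different measures as well: an institutional formula or GFR at entry, Cockcroft-Gault or a urine collection for the dose rule. One patient could then sit in different bands under the two rules.

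**Working it through.** **Thresholds side by side**

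| CrCl at entry (mL/min) | Table 1 | Section 6.2.1.3 and Table 3b |
|---|---|---|
| ≥51 | Eligible | Matches the stated inclusion threshold |
| 31–50 | Eligible on either route | Below the stated threshold; 200 mg twice daily recommended only if it arises on study |
| Exactly 30 | Eligible on either route | Severe, unstudied; stopping recommended |
| Below 30 | Eligible if creatinine ≤1.5 × ULN | Severe, unstudied; stopping recommended |

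The two floors differ by 51 − 30 = 21 mL/min. The daily doses differ by 2 × 300 − 2 × 200 = 600 − 400 = 200 mg.

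**Can the creatinine route reach below 51?** The documents give no renal data, so this shows reach, not frequency. Assumptions, none from the documents: ages 30, 40, 50, 60 and 70; weights 50, 60, 70, 80 and 90 kg (25 unweighted cells); creatinine ULN 1.0 mg/dL, varied to 0.9 and 1.1. For women, Cockcroft-Gault is

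CrCl = (140 − age) × kg × 0.85 / (72 × creatinine).

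*Creatinine 1.0 × ULN, ULN 1.0 mg/dL:*
- age 60, 50 kg: 80 × 50 × 0.85 / 72 = 47.2
- age 70, 50 kg: 70 × 50 × 0.85 / 72 = 41.3
- age 70, 60 kg: 70 × 60 × 0.85 / 72 = 49.6
- next lowest, age 50, 50 kg: 90 × 50 × 0.85 / 72 = 53.1

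So 3 of 25 cells are below 51 and none is ≤30.

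*Creatinine 1.5 × ULN (the Table 1 limit), ULN 1.0 mg/dL:* at age 60, 60 kg, CrCl = 80 × 60 × 0.85 / (72 × 1.5) = 37.8; at age 70, 50 kg, 70 × 50 × 0.85 / 108 = 27.5.

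| Creatinine | ULN (mg/dL) | Cells below 51 | Of these, ≤30 |
|---|---|---|---|
| 1.0 × ULN | 0.9 | 1 of 25 | 0 |
| 1.0 × ULN | 1.0 | 3 of 25 | 0 |
| 1.0 × ULN | 1.1 | 4 of 25 | 0 |
| 1.25 × ULN | 1.0 | 7 of 25 | 0 |
| 1.5 × ULN | 0.9 | 11 of 25 | 0 |
| 1.5 × ULN | 1.0 | 15 of 25 | 1 |
| 1.5 × ULN | 1.1 | 17 of 25 | 2 |

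Every cell passes Table 1 on creatinine alone. The rows above 1.0 × ULN count only if such patients may be dosed, which depends on a sentence taken up in the objection.

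**The case against.** Three controls act before dosing. Exclusion 21 (Section 5.1.2) lets the investigator exclude a patient for a laboratory abnormality or because taking part is not in her interest. Section 6.1.3.2 requires laboratory results to be judged acceptable before each dose. Criterion 10 adds "Labs must also fall within normal limits prior to infusion". Read literally, that last sentence bars infusion when creatinine exceeds ULN. Since olaparib begins right after the first infusion (Section 5.2.1), neither the CrCl ≥30 route nor the 1.25 × and 1.5 × rows would reach dosing.

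Much of this stands. An investigator can stop a patient near 30 mL/min before her first tablet, and the literal reading cuts the illustration to 3 of 25 cells, none ≤30. But the preceding sentence equates normal values with those in Table 1, so the looser reading remains open. None of the three controls gives a CrCl figure or a starting dose, and 3 cells stay below 51 even on the strict reading. Table 1's closing note, "laboratory value requirements should be adapted according to local regulations and guidelines for the administration of specific chemotherapies", supplies no figure either.

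A reader might infer three stronger things:
- **That about 60% of patients are affected (15 of 25).** The cells are unweighted and assumed, and that row needs both creatinine at the limit and the looser reading.
- **That the protocol doses above its own recommendation at entry.** It is silent on an entry dose; the 200 mg recommendation is for later impairment and is discretionary.
- **That sites will enrol to different floors.** Section 6.2.1.3 acts only after entry, so a site would screen from Table 1.

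**Conclusion.** The inconsistency holds. The stated inclusion threshold of 51 mL/min appears in no criterion, and the dose rule built around it leaves patients who enter at 31–50 to start at 600 mg/day without guidance. Table 1 also admits a CrCl of exactly 30, a single boundary value that Section 6.2.1.3 treats as severe.

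These conclusions come from the text alone. The cell counts rest on assumed ages, weights and ULN and show only that the gap can be reached with creatinine no higher than ULN. How many of the 48 patients it would touch cannot be estimated from the documents. Pre-dose judgement limits the harm without closing the gap. The matter is one of eligibility and dosing safety and should be corrected; the sample size, the error rates and the iORR analysis do not depend on it.

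**What to change.** **Preferred.** Require CrCl ≥51 mL/min in Table 1 on both routes, and name Cockcroft-Gault in footnote b so that entry and dosing share a formula. Section 6.2.1.3, Table 3b and the Table 2 starting dose then fit together, and no entry-dose rule is needed. No new test is required: creatinine (Table 10) and weight (Section 6.1.2.4) are already collected. The cost is accrual. If a share s of otherwise eligible patients is below 51, 48/(1 − s) must be screened to enrol 48. The documents do not give s; for assumed values of 5%, 10% and 20% this is 48/0.95 = 50.5, 48/0.90 = 53.3 and 48/0.80 = 60, so 51, 54 and 60 patients.

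**If the sponsor means to admit CrCl 31–50.** Set a floor of ≥31 by Cockcroft-Gault on both routes, correct the 51 in Section 6.2.1.3, and reword its retest trigger to work for patients who enter below 51. State a starting dose of 200 mg twice daily for entry CrCl 31–50, with two provisos:
- It must not exceed the dose in force. If the six-patient rule has moved later patients to 300 mg once daily, 200 mg twice daily (400 mg/day) would give renally impaired patients more than the others.
- Section 6.2 allows no reduction below 200 mg twice daily, so these patients have no toxicity step left.

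Under this option, patients in the band contribute lower olaparib exposure to the iORR estimate, and those at ≤30 become ineligible. Either option is an amendment to wording.
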